### F] Recruitment strategy:

The principal investigator will recruit the patients from the clinic of Orthodontic department, Faculty of Oral and Dental Medicine- Future University in Egypt. Screening of patients will continue until the total number of participants for the study is collected.

### II) Assignment of interventions

### **A]** Sequence generation:

The supervisor of the study will apply Computer generated random numbers to randomly assign patients to group A (En-masse) or B (two steps) using Microsoft Office Excel 2007 sheet. The patient numbers will be written in the first column and the supervisor will select function RAND to generate the randomization number in the second column. These numbers will be sorted according to the randomization number so the first column numbers will be randomly distributed.

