# Intervention:

Distalization of maxillary first molars using infra-zygomatic gear distalizer after extraction of maxillary third molars.

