# **Comparator:**

Distalization of maxillary first molars using infra-zygomatic mini-implants as anchorage unit without extraction of maxillary third molars.

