### **Participant timeline:**

1. The principal investigator will screen the potential patients through careful clinical examination of patients at the orthodontic department, Faculty of Oral and Dental Medicine, Future University in Egypt.

2. All recruited patients should fulfil the previously mentioned inclusion and exclusion criteria.

3. Every participant will be asked to sign an informed consent before the beginning of the study.

4. After patient's enrolment, each participant will be asked for preintervention records to ensure proper diagnosis.

[figure not shown]
5. The principal investigator will randomly allocate the patients to one of the intervention groups.

**6.** After patient's enrolment, pre-intervention records will be taken for each participant to ensure proper diagnosis (T0).

7. Every 4 weeks Each patient will have follow up visit, for appliance activation, uptake of impression for interim records and checking for mini-screws stability (T1-T7).

**8.** Post- records for each participant will be taken after duration of eight months (T8) at the same visit of appliance removal.

[figure not shown]
**9.** The principal investigator will continue the normal orthodontic treatment and achieved proper finished occlusion for every patient after the end of the study.

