### **B]** Allocation concealment mechanism:

The Co-supervisor of the study ([name]) will write the randomization numbers of the patients on opaque white papers folded three times to form sealed envelopes and store it inside a box. The codes for randomization will be securely held at the secretary's office.

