### **C] Implementation**

At the time of intervention, the main operator will send the patient to the secretary's office. Then, the assigned employee will open the box and ask the patient to select one envelope. The main operator will contact the supervisor to know the order and then the main operator will allocate each patient to assign each participant for the corresponding intervention either (extraction or non-extraction) according to the list of codes of randomization.

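### The randomisation list is written for arms that are not in this trial, no key links a code to extraction or non-extraction, and the allocation steps leave concealment unassured

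*Combined protocol and SAP*

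**What the plan says.** **The arms.** The PICO section defines the intervention as "Distalization of maxillary first molars using infra-zygomatic gear distalizer after extraction of maxillary third molars" and the comparator as "Distalization of maxillary first molars using infra-zygomatic mini-implants as anchorage unit without extraction of maxillary third molars". Study design gives a 1:1 ratio, and Sample size calculation gives 11 per group.

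**The list.** Sequence generation has the supervisor "randomly assign patients to group A (En-masse) or B (two steps", in an Excel sheet. Patient numbers go in one column and RAND values in the next, and then: "These numbers will be sorted according to the randomization number so the first column numbers will be randomly distributed". The description stops there.

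**The device.** Under Allocation concealment mechanism, a co-supervisor writes the randomization numbers on "opaque white papers folded three times to form sealed envelopes", which are kept in a box. The codes are held at the secretary's office.

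**The act of allocation.** Under Implementation, an employee opens the box and the patient picks one paper. Then the "main operator will contact the supervisor to know the order and then the main operator will allocate each patient" to extraction or non-extraction, following the code list. The Participant timeline (step 5) says instead: "The principal investigator will randomly allocate the patients to one of the intervention groups". Blinding states that the operator and the patient know the treatment.

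**The concern.** Sequence generation is the only instruction for making the list, and it names two arms that belong to another comparison. Statistical Analysis also refers to arms from elsewhere (friction and frictionless retraction), so template carry-over is the likely cause. Even so, the plan does not fix in advance which arm a given number leads to. If that link is settled only when a number is turned into a treatment, it can be settled with the patient's records in view: timeline step 4 (records) precedes step 5 (allocation).

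In a small trial with open treatment, a list fixed beforehand and hidden from those who enrol and treat is the main protection against selection bias. Blinded reading of models and CBCT protects the measurement, but it cannot repair arms that differed at entry.

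**Working it through.** **1. The plan's own figure.** Inputs from Sample size calculation: means (SD) 3.17 (0.81) and 4.32 (0.79) mm, alpha 0.05, power 80%.

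- Pooled SD = √[(0.81² + 0.79²)/2] = 0.800 mm.
- Effect size = (4.32 − 3.17)/0.800 = 1.15/0.800 = 1.437, as stated.
- Two-sided t-test, noncentral t: 8 per arm gives 76.2% power and 9 per arm gives 81.6%. The stated 9 per group (18 in all) reproduces.
- 1 − 9/11 = 18%, so 11 per group allows for about 18% loss.

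The present point leaves this calculation untouched.

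**2. The labels and the key, side by side.**

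| Section | How the arm is identified |
|---|---|
| Intervention / Comparator | with / without third molar extraction |
| Sample size calculation | TME / TMP |
| Sequence generation | A = en-masse, B = two steps |
| Allocation concealment mechanism | a randomization number |
| Implementation | extraction / non-extraction, from a code list |

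No section joins the third or fourth row to the others. Sorting patient numbers by RAND produces an order. It does not produce arms until a rule is added, such as first 11 to one arm, and none is given.

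**3. Two randomising steps.** A sorted list fixes an order in advance. A patient's pick from a box creates a new order on the day. Either could set the arm. The text uses both and does not say which governs.

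**4. Who allocates.** The timeline says the principal investigator, who also screens (step 1) and recruits (Recruitment strategy). Implementation says the main operator, after contacting the supervisor. The documents do not say whether these are one person.

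**5. What the unstated restriction would mean for 22 patients.**

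- Unrestricted (a coin toss for each patient): P(exactly 11:11) = C(22,11)/2²² = 705,432/4,194,304 = 16.8%. P(8:14 or worse) = 28.6%. An 8:14 split costs little precision: √(1/8 + 1/14) = 0.443 against √(2/11) = 0.426, a standard error about 4% larger. It does leave one arm below the planned minimum of 9 before any dropout.
- Fixed at 11:11, past assignments known: the best guess each time is right on average 11 + ½(2²²/C(22,11) − 1) = 11 + ½(5.946 − 1) = 13.5 times in 22, or 61% against 50% by chance. On average the last 2 × 11/12 = 1.8 assignments are certain.

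**6. Illustration only: one swapped pair.** If two patients whose expected distalization differs by Δ change places, the between-arm difference moves by 2Δ/11. Δ is an assumption; the documents give no basis for it.

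| Δ | Shift | Share of 1.15 mm |
|---|---|---|
| 0.4 mm (0.5 SD) | 0.07 mm | 6% |
| 0.8 mm (1 SD) | 0.15 mm | 13% |
| 1.2 mm (1.5 SD) | 0.22 mm | 19% |

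The standard error of the difference at 11 per arm is 0.80 × 0.426 = 0.34 mm, so the largest shift shown is about 0.64 standard errors.

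**The case against.** The strongest reply is that the plan does conceal. The papers are opaque and said to be sealed. They carry numbers, not arm names, so a paper read early reveals nothing without the list. A co-supervisor prepares them, the codes are kept at the secretary's office, the patient draws in front of an employee, and consent comes before allocation. Implementation names the two correct treatments, so the wrong labels may be no more than a drafting slip. On a natural reading, the supervisor, who made the list, discloses the assignment and the operator only carries it out.

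Much of this stands, and it rules out several stronger readings that a reader might infer:

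- *Allocation is not concealed.* The device just described contradicts this.
- *The enrolling operator decodes the draw.* Recruitment is given to the principal investigator and the draw to the main operator, and nothing says they are the same person or that the operator holds the list.
- *The custody statements conflict.* Codes stored in one office are compatible with a supervisor who can report the order.
- *The trial's arms are undefined.* They are named at Implementation; only the link from code to arm is missing.

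The reply does not supply that link, the 1:1 rule, a single allocator, sequential numbering or a log. Hiding a number protects less when the text does not fix the arm it stands for.

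**Conclusion.** The point holds as a defect in the operative randomisation text. The arm labels are wrong, the code-to-arm key and the 11:11 restriction are absent, two randomising steps compete, and two sections name different allocators. Concealment is described but not assured, because the papers are not sequentially numbered, the draw is not logged and the treating operator applies the code list.

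The documents show no actual bias and give no means of estimating one. The predictability and imbalance figures depend on which scheme is meant, which the plan does not say. The swap table (6% to 19% of the target difference) assumes that someone can foresee distalization and is willing to override the draw; no section supports either, so it should carry no weight in judging severity. The conclusion rests on the text alone: two figures in the Participant timeline could not be read. This should be corrected before the first patient is allocated.

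**What to change.** - **Sequence generation:** name group A as third molar extraction (TME) and group B as third molars present (TMP). State the key from code to arm and the restriction that gives 11:11. Freeze the list before the first patient.
- **Allocation concealment mechanism:** use 22 sequentially numbered, opaque, sealed envelopes held at the secretary's office, in place of folded papers drawn from a box. The frozen list then sets the arm.
- **Implementation:** once eligibility and consent are confirmed, the employee opens the next envelope, logs it and tells the operator. Neither the operator nor the principal investigator holds or consults the list.
- **Participant timeline, step 5:** amend to match.

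The cost is protocol wording, 22 envelopes and a log, with the same staff. One drawback remains: with a fixed 11:11 list and open treatment, anyone tracking past assignments can predict the last few (1.8 on average are certain). If envelopes hold the arm name, sealing and the log matter more than with number-only papers.

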### **B]** Allocation concealment mechanism:

The Co-supervisor of the study ([name]) will write the randomization numbers of the patients on opaque white papers folded three times to form sealed envelopes and store it inside a box. The codes for randomization will be securely held at the secretary's office.

### **C] Implementation**

At the time of intervention, the main operator will send the patient to the secretary's office. Then, the assigned employee will open the box and ask the patient to select one envelope. The main operator will contact the supervisor to know the order and then the main operator will allocate each patient to assign each participant for the corresponding intervention either (extraction or non-extraction) according to the list of codes of randomization.

### **D]Blinding:**

Because both the operator and the patient are aware of the clinical intervention, double-blinding is not feasible. However, the digital dental models and CBCT will be assessed blindly by a trained external assessor.

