# **Outcome measure(s):**

	Outcome name	Measuring device	Measuring unit
Primary outcome	The total anteroposterior distance moved by the maxillary first molars.	Digital models using 3- shape scanner and program.	mm

		CBCT images using Anatomage software.	mm
Secondary outcomes	1-Maxillary first molar distalization rate.	Digital models using 3 shape scanner and program.	mm/month
	2-Maxillary first molar rotation	Digital models using 3 shape scanner and program.	Degree
	3- Intermolar width	Digital models using 3 shape scanner and program.	mm
	4-Maxillary first molar tipping and torque	CBCT images using Anatomage software.	Degree
	5-Maxillary first molar vertical changes	CBCT images using Anatomage software	mm

	6- Total anteroposterior distance moved by maxillary first and second premolars.	Digital models using 3 shape scanner and program.	mm
	7- Maxillary second molar tipping.	CBCT images using Anatomage software	Degree
	8-Maxillary third molar tipping	CBCT images using Anatomage software	Degree
	9-Maxillary third molar vertical changes	CBCT images using Anatomage software	mm
	10-Maxillary four incisors anteroposterior and vertical linear measurements.	CBCT images using Anatomage software	mm
	11- Maxillary four incisors torque.	CBCT images using Anatomage software	mm

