#### **Material and Methods**

### I) Participants, Interventions, and Outcomes

### A) Study Setting:

The study will be performed in the clinic of the Orthodontic Department at the Faculty of Oral and Dental Medicine, Future University in Egypt. The recruited sample would be from the Egyptian urban and rural population.

B) Eligibility: for the participants include the following:

(1) Adolescent patients aged 16-19 years.

(2) skeletal Class I ( $0^{\circ} < ANB < 4$ ).

(3) bilateral Class II molar relationship. defined by at least an end-to-end molar relationship.

(4) normal vertical growth pattern.

(5) full permanent dentition with unerupted upper third molars.

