### **O** Clinical Procedure:

After taking pre-treatment records, every patient will receive:

- The third molars will be extracted surgically in the third molar extraction group four weeks before intervention commenced.
- Proper disinfection will be performed with a local disinfectant, BETADINE povidone-iodine 10%, at the area of mini-implant insertion.
- Two infra zygomatic mini-implants will be placed (Screw Tomas pin 10mm, dentaurum, Germany).
- Bands will be cemented to the upper first molars.
- The inner bow (1.2mm) is a modified version of the inner part of a conventional face bow. Two hooks were soldered onto the inner bow distal to the lateral incisor teeth regions. A U loop at the first premolar region and bends acting as a mesial stop will be bent in front of the maxillary first molars.

- The inner bow will be adjusted to the headgear tubes on the maxillary first molar bands, as the anterior component of the inner bow is 3 mm free from the labial surface of the anterior teeth.
- A distalization force of 300 gm/per side was applied to the maxillary molars via a closed coil spring (Tomascoil spring, Dentourum, Germany). According to the desired activation length, the distal end of the coil spring was set to the IZ mini-screw, while the mesial end was linked to the wire framework hook either directly or with a 0.01-inch stainless-steel ligature

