### 3) Methods of measuring of all outcomes:

Linear and angular measurements will be made on the pre, post and follow-up digital models and on the pre-and post distalization CBCT to assess the dental changes in intervention group.

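### Blinded CBCT reading is not achievable as described, because an unmasked post-distalization scan shows whether the third molars were extracted and no masking is specified

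*Combined protocol and SAP*

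**What the plan says.** The Blinding section accepts that operator and patient will know the treatment. It places all protection on the reading stage: "the digital dental models and CBCT will be assessed blindly by a trained external assessor". It does not say how the CBCT reader is kept unaware of the arm.

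The passages that bear on this are:

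- **Eligibility** (under Study Setting) requires "full permanent dentition with unerupted upper third molars" in every participant.
- **Intervention** in the PICO section: "Distalization of maxillary first molars using infra-zygomatic gear distalizer after extraction of maxillary third molars". The comparator keeps the third molars.
- **Clinical Procedure**, which starts once pre-treatment records have been taken: "The third molars will be extracted surgically in the third molar extraction group four weeks before intervention commenced".
- **Methods of measuring of all outcomes** has measurements made "on the pre-and post distalization CBCT to assess the dental changes in intervention group".
- **Outcome measure(s)** lists the primary outcome, "The total anteroposterior distance moved by the maxillary first molars", under two instruments: "Digital models using 3- shape scanner and program" and CBCT. Neither is named as decisive. The CBCT secondary rows include "8-Maxillary third molar tipping" and third-molar vertical change (rows 8 and 9).
- **Data collection methods** and **Statistical Analysis** (part III, A and C) have the principal investigator identify landmarks on models and CBCT and extract the CBCT data.

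**The concern.** Assessor blinding is the only blinding the trial claims. For CBCT, the randomised contrast is itself an anatomical feature of the image, lying next to the teeth being measured. A coded ID hides the patient's name but not the third molars.

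The readings depend on landmarks, reference lines and planes that a person identifies. The Sample size calculation section also gives a direction that a reader might expect: 4.32 mm in one group and 3.17 mm in the other (labelled TME and TMP, which I read as third molars extracted and present). If placement drifts with knowledge of the arm, the between-arm CBCT differences carry detection bias while the report describes them as blind. The reliability checks in Assessors Reliability would not reveal this. They look at agreement within and between examiners, with attention to disagreements above one millimetre, and a bias shared by readers who all see the arm produces no disagreement.

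**Working it through.** **Step 1: does the scan reveal the arm?** The blinding claim contains no figure, so the check is to set the passages side by side.

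| Question | What the documents give | Consequence |
|---|---|---|
| Third molars at entry? | Present and unerupted in all (Eligibility) | Arms look alike before extraction |
| What differs afterwards? | Removed in one arm only (Intervention, Clinical Procedure) | Third-molar status is the allocation |
| When is CBCT taken? | Before and after distalization (Methods of measuring) | The post scan follows the extraction |
| Is the third-molar region in the field? | Rows 8 and 9 are read on CBCT | Yes, at least in the non-extraction arm |
| Is masking described? | None found; Confidentiality provides a coded ID only | Nothing hides the region |

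On an unmasked post scan, third molars present means non-extraction and absent means extraction. The pre scan does not reveal the arm if it belongs to the pre-treatment records, which come before extraction. The Methods of measuring section refers to a single group, but I read CBCT as taken in both arms: rows 8 and 9 can be followed to the end only in the non-extraction arm, and the other rows need both arms for a comparison.

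**Step 2: which outcomes are affected?** The CBCT rows are the second instrument for the primary outcome and secondary rows 4, 5, 7, 8, 9, 10 and 11. Rows 8 and 9 have post-distalization values in one arm only, so they are not between-arm comparisons. That leaves the CBCT primary measure and five rows:

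- row 4: first-molar tipping and torque
- row 5: first-molar vertical change
- row 7: second-molar tipping
- row 10: incisor linear measurements
- row 11: incisor torque

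**Step 3: the plan's own figure.** Inputs are from Sample size calculation.

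- Pooled SD = √((0.81² + 0.79²)/2) = 0.800 mm.
- Difference = 4.32 − 3.17 = 1.15 mm.
- Effect size = 1.15/0.800 = 1.437, as stated.
- A two-sided two-sample t-test at 5% with 80% power needs 8.7, rounded up to 9 per group, as stated. Exact power is 81.6% at 9 and 89.3% at 11 per group.

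The sample size reproduces, and this point does not alter it.

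**Step 4: illustration of size.** The documents give no figure for reading bias. Assume an arm-dependent shift b in first-molar anteroposterior movement, SD 0.80 mm, 11 per group, no true difference, and a two-sided two-sample t-test. The noncentrality is (b/0.80) × √(11/2) on 20 degrees of freedom.

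| Assumed b (mm) | b/1.15 | False-positive rate (nominal 5%) |
|---|---|---|
| 0.1 | 9% | 5.9% |
| 0.2 | 17% | 8.6% |
| 0.4 | 35% | 20.1% |
| 0.5 | 43% | 28.7% |

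This table applies only to first-molar anteroposterior movement read on CBCT. The 1.15 mm difference cannot scale tipping or torque, or the vertical and incisor measures, so no magnitude is shown for the five secondary rows.

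**The case against.** The strongest reply is that the Blinding section states an aim and leaves the method open. Volumes can be cropped, the incisors lie far from the third-molar site, and a restricted view could cover them. A reader might infer that blind CBCT reading is impossible, or that every CBCT outcome will in fact be read with the arm visible. The documents support neither. Masking could restore blinding, and actual conduct cannot be read from silence. What stands is narrower: as described, with no masking step, the claim cannot be relied on.

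A second reply is that the primary outcome survives. Digital models are listed first for it, and the pilot means are not attributed to CBCT. This is largely right and keeps the point below the most serious grade. Two limits remain. The plan does not say which instrument decides the primary outcome. And the models are safe only while the third molars stay unerupted: patients are 16 to 19, the Statement of the problem gives 20 years as the average age of third-molar alveolar eruption, and treatment can last eight months, so some could emerge in the non-extraction arm.

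Third, no document says that the external assessor knows the pilot direction, and the stated hypothesis is the null. That is fair. It is why the figures above are an illustration and not an estimate.

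Finally, masking alone would not deliver blinding while the principal investigator places landmarks and extracts the CBCT data. This stands, and the fix must cover it. The converse also holds: giving the reading to the external assessor would not help if the scans stay unmasked.

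**Conclusion.** The point holds in limited form. Followed exactly, the Blinding section does not give the CBCT outcomes the protection it claims, because the unmasked post-distalization scan displays the randomised contrast. The reach is the CBCT version of the primary outcome and secondary rows 4, 5, 7, 10 and 11. The model-based primary measure is outside this mechanism while the third molars remain unerupted.

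The size of any bias is unknown. The range of 17% to 35% of the pilot difference rests wholly on an assumed shift of 0.2 to 0.4 mm, for one outcome. The conclusion itself rests on the third molars being visible in the post-distalization volume, which rows 8 and 9 require for the non-extraction arm, and on the absence of any described masking. It should be fixed, but it does not undermine the trial's main comparison if the model measurement carries it.

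**What to change.** 1. In Outcome measure(s) and the Outcomes section, name the digital-model measurement, read blind, as the primary measure. Present the CBCT measurement of the same movement as supportive.
2. In the Blinding section, specify that someone other than the reader crops or masks each pre and post CBCT volume distal to the second molars and assigns a code. The colleague outside the research team who enters the data could do this. The reader works through the coded volumes in random order. Third-molar tipping and vertical change are read last, in a separate pass on unmasked scans.
3. Where masking is not done or fails, state that the CBCT outcome is assessed unblinded. Second-molar tipping is the likeliest case, because the third-molar site is adjacent to that tooth.
4. Reconcile the Blinding section with Data collection methods and Statistical Analysis, so that the external assessor, not the principal investigator, places the landmarks on models and CBCT.

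The cost is a wording change and a little image preparation per scan, with no new scan, visit or reader. The downside is the care needed in setting the crop line near the second-molar roots. The change should be made before any post-distalization scan is read, since an unmasked reading can be made blind later only by reading again.
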